#### 6.5.1. Prohibited During the Study

- Prophylactic antipyretics and other pain medications to prevent symptoms associated with the investigational product are not permitted.
- On the day of planned vaccination, if the participant has received antipyretics or other pain medications prior to a planned administration of the investigational product, vaccination should be temporarily delayed as specified in Section 5.5.1.
- Receipt of any investigational vaccines, drugs, or medical devices is prohibited during study participation.
- Receipt of any blood products, including immunoglobulin.
- Nonstudy meningococcal vaccine groups A, C, W, or Y.
- Nonlive or live nonstudy vaccines are not permitted 14 and 28 days, respectively, before or after any study vaccination.

- Tetanus-containing vaccines are not permitted 30 days before any study vaccination.
- Intramuscular/sublingual allergen therapy is not permitted within 14 days of any study vaccination.
- Systemic (oral, intravenous, or intramuscular) corticosteroid therapy within 28 days of any study vaccination.

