| Record and report SAEs and NDCMCs f | X             |                     |               | X                   |

- a. Only concomitant medications used to treat SAEs and NDCMCs will be recorded.
- b. Blood sample will be collected prior to vaccination.
- c. Remind the participant's parent(s)/legal guardian(s) that the use of prophylactic antipyretic/pain medication, while permitted, is not recommended on the day of investigational product administration (before or after vaccination).
- d. The participant's parent(s)/legal guardian(s) will record local reactions and systemic events in an e-diary for the 7 days following each dose of Nimenrix. Use of antipyretic/pain medications will also be collected daily in an e-diary for 7 days after vaccination. The participant's parent(s)/legal guardian(s) will be instructed to contact the study staff if the participant experiences redness or swelling >14 caliper units, severe pain at the injection site, or a fever >40.0°C or has an emergency room visit or hospitalization.
- e. Designated site staff will review e-diary data online at frequent intervals (daily is optimal) for the 7 days following each dose of Nimenrix to evaluate participant compliance and as part of the ongoing safety review.
- f. An NDCMC is defined as a disease or medical condition, not previously identified, that is expected to be persistent or otherwise long-lasting in its effects.

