# 3. OBJECTIVES, ESTIMANDS, AND ENDPOINTS

|   | Objectives   | Estimands  |   | Endpoints   |  |
|---|--|--|---|---|--|
|   | Primary (Safety):  | Primary (Safety):  |   | Primary (Safety):   |  |
| • | To describe the safety of 2 doses of Nimenrix when administered in healthy infants at 3 and 12 months of age.  | 
 
In participants receiving Dose 1 and 2:
 
The percentage of participants reporting local reactions, systemic events, and use of antipyretic medication within 7 days after Dose 2 (Visit 3, 12 months of age) of Nimenrix.
 
The percentage of participants reporting at least 1 AE, at least 1 SAE, and at least 1 NDCMC during the following time period: 
 
Within 30 days after Dose 2 (Visit 3, 12 months of age) of Nimenrix.
 
 
 
The percentage of participants reporting at least 1 immediate AE after Dose 2 (Visit 3, 12 months of age) of Nimenrix.
 
  | • | Local reactions (redness, swelling, and pain at the injection site). Systemic events (fever, decreased appetite, drowsiness, and irritability). AEs. SAEs. NDCMCs.                    |  |
|   | Primary (Immunogenicity):  | Primary (Immunogenicity):  |   | Primary (Immunogenicity):   |  |
| • | To describe the immune response for N meningitidis serogroups A, C, W-135, and Y induced by 2 doses of Nimenrix administered at 3 and 12 months of age. | In participants receiving both doses of Nimenrix and who are in compliance with the key protocol criteria (evaluable participants):  • Percentage of participants with rSBA-MenA, rSBA-MenC, rSBA-MenW-135, and rSBA-MenY titers ≥1:8 for each serogroup at baseline (Visit 1, 3 months of age), at 1 month after Dose 1 (Visit 2, 4 months of age), at Dose 2 (Visit 3, 12 months of age), and at 1 month after Dose 2 (Visit 4, 13 months of age) of Nimenrix.  • rSBA-MenA, rSBA-MenC, rSBA-MenW-135, and rSBA-MenY GMTs for each serogroup at baseline (Visit 1, 3 months of age), at 1 month after Dose 1 (Visit 2, 4 months of age), at Dose 2 (Visit 3, 12 months of age), and at 1 month after Dose 2 (Visit 4, 13 months of age) of Nimenrix. | • | rSBA titers for each of
the MenA, MenC,
MenW-135, and MenY
serogroups.   |  |
|   | Secondary:   | Secondary:   |   | Secondary:  |  |

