# 5.5.1.1. Criteria for Temporarily Delaying Vaccine Administration

- Current febrile illness (temperature ≥38.0°C) or other acute illness within 48 hours before investigational product administration.
- Participant has received antipyretic medication or other pain medication on the planned day of vaccination.
- Participant has received any nonlive vaccine (or intramuscular/sublingual allergen immunotherapy) within 14 days, or any live vaccine within 28 days, before investigational product administration.
- Participant has received tetanus-containing vaccines within 30 days before investigational product administration.
- Participant is less than 5 days into a course of systemic antibiotic therapy.
- Participant has received systemic (oral, intravenous, or intramuscular) corticosteroid therapy within the previous 28 days.

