#### 6.5.2. Permitted During the Study

- Nonstudy vaccines used in the event of a disease outbreak or pandemic are allowed. However, while prioritizing standard clinical care, efforts should be made not to administer nonstudy vaccines within 14 days (for nonlive vaccines) or 28 days (for live vaccines) prior to study vaccine administration, as specified below.
- Nonstudy vaccines (other than meningococcal vaccine groups A, C, W, or Y) that are part of recommended immunization schedules are allowed any time during the study but should not be administered within 14 days (for nonlive vaccines) and 28 days (for live vaccines) of study vaccine administration. Tetanus-containing vaccines are allowed any time during the study (and can be given at the same time as study vaccine) but should not be administered within 30 days before study vaccine administration.
- Antipyretics and other pain medications to treat symptoms associated with the investigational product are permitted.
- A local anesthetic may be used at the site of the blood draw.
- Topical antibiotics are permitted.
- Topical and inhaled corticosteroids are permitted.

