## 8.2.2.3. Use of Antipyretic/Pain Medication

The participant's parent(s)/legal guardian(s) will be asked to record the use of antipyretic/pain medication (Yes/No) in the e-diary (in a provisioned device or application on a personal device) in the evening, daily, for 7 days after each investigational product.

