- Issue the participant's parent(s)/legal guardian(s) an e-diary (device or application). Provide instructions on use and completion of the e-diary. Ask the participant's

parent(s)/legal guardian(s) to complete the e-diary from Day 1 to Day 7, with Day 1 being the day of vaccination.

- Ask the participant's parent(s)/legal guardian(s) to contact the site staff or investigator as soon as possible during the 7-day postvaccination period if the participant has a fever >40.0°C, redness and/or swelling at the injection site measuring >14 measuring device units (>7 cm), or severe injection site pain (causes limitation of limb movement) to determine if the event requires further assessment by the investigator.
- Ask the participant's parent(s)/legal guardian(s) to contact the site staff or investigator as soon as possible if any significant illness or medical event (eg, emergency room or hospitalization) occurs.
- Provide the participant's parent(s)/legal guardian(s) with the participant contact card containing the study and investigator information (see Section 10.1.10).
- Inform the participant's parent(s)/legal guardian(s) that the use of prophylactic antipyretic/pain medication, while permitted, is not recommended on the day of investigational product administration (before or after vaccination).
- The investigator or an authorized designee completes the CRF and the source documents and updates the investigational product accountability records.
- The investigator or appropriately qualified designee reviews the e-diary data online at frequent intervals for the 7 days following vaccination to evaluate participant compliance and as part of the ongoing safety review.

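### Protocol 6.5.1 bars prophylactic antipyretics, but the schedule footnotes and vaccination-visit instructions have staff tell parents they are permitted, leaving use after the dose unresolved

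*Protocol*

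**What the plan says.** The rule for concomitant therapy is in Protocol 6.5.1: "Prophylactic antipyretics and other pain medications to prevent symptoms associated with the investigational product are not permitted". It carries no time limit. Section 6.5.2 allows the same medicines for a different purpose: "Antipyretics and other pain medications to treat symptoms associated with the investigational product are permitted". SAP 3.6.2 repeats that treatment permission and adds none for prevention.

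The instructions that staff work from say something else. In Protocol 1.3, footnote c has staff remind parents that "the use of prophylactic antipyretic/pain medication, while permitted, is not recommended on the day of investigational product administration", and it covers both sides of the injection. Section 8.11.1 (Visit 1) says that prophylaxis, "while permitted, is not recommended on the day of investigational product administration (before or after vaccination"). The same sentence stands in 8.11.3 (Visit 3) and in footnote c of SAP Table 4.

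One further rule applies before the dose. Section 5.5.1.1 lists as a reason to delay vaccination: "Participant has received antipyretic medication or other pain medication on the planned day of vaccination".

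On endpoints, the primary safety estimand in Protocol Section 3 includes "The percentage of participants reporting local reactions, systemic events, and use of antipyretic medication within 7 days after Dose 2". The Dose 1 equivalent is secondary. On data capture, parents are asked to "record the use of antipyretic/pain medication (Yes/No) in the e-diary" (8.2.2.3), and for the case report form, footnote a of the schedule says "Only concomitant medications used to treat SAEs and NDCMCs will be recorded".

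**The concern.** The same act is barred in the therapy section and allowed in the text that staff pass on to parents. A site that follows the visit procedures faithfully would permit what 6.5.1 prohibits.

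This matters because the act bears directly on what is measured. An antipyretic or painkiller given in advance can suppress fever, pain and irritability in the week after the dose. The same dose of medicine counts as antipyretic use, which is itself reported. The study has one arm, so there is no control group in which the same practice would show.

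A second consequence concerns the analysis sets. SAP Section 4, criterion 5, requires that no prohibited medication was received. The plan does not say how that criterion treats an infant given prophylaxis that staff had described as permitted.

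**Working it through.** The point rests on text rather than on a stated figure, so the check sets the provisions side by side.

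1. **Scope of the two rules.** Section 6.5.1 covers prevention of reactions to the study vaccine, at any time, and bars it. The four instructions (Protocol 1.3 footnote c, 8.11.1, 8.11.3, SAP Table 4 footnote c) cover prophylaxis for any purpose on the day of the dose, before or after it, and allow it with discouragement. They overlap on prophylaxis against Nimenrix reactions on the vaccination day. There the count is one prohibition against four permissions.

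2. **Before the dose.** Section 5.5.1.1 and the second bullet of 6.5.1 delay vaccination if such medication was given earlier that day. Whatever parents were told, the outcome is defined.

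3. **After the dose.** A delay rule can no longer act. Sections 6.5.2 and SAP 3.6.2 speak only of treatment. Nothing else in the two documents settles the matter, and neither says which section takes precedence. Section 8 of the protocol calls for adherence to the schedule, which points sites to the permissive wording.

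4. **Status of the texts.** The protocol is the original and the SAP is version 1, so none of this is superseded wording.

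5. **Direction of effect.** Write p for the fever rate without prophylaxis, f for the share of infants given prophylaxis after the dose and r for the relative reduction in fever among them. Observed fever is p × (1 − f × r), so it falls if r is above zero. Antipyretic use rises by the share of infants who would otherwise have had none. The two components move in opposite directions.

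6. **Size of effect.** The documents give none of p, f or r. The quantity that the wording controls is also not f but the part of f that exists because parents were told it is permitted. That is not given either.

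7. **Whether the data could separate it afterwards.**
   - The e-diary holds a daily Yes/No with no reason for use.
   - The case report form takes only medication for SAEs and NDCMCs.
   - The separate antipyretic summary in SAP 6.5.5 concerns the day before vaccination.
   - SAP 3.5.2.1 to 3.5.2.3 derive symptoms and antipyretic use by day, so use on a symptom-free day can be counted. This is an imperfect proxy: it misses prophylaxis followed by breakthrough fever and includes use for other reasons.

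**The case against.** The strongest reply is that the practical gap is narrow. The four instructions discourage prophylaxis, the delay rule deals with use before the dose, and the study is descriptive with no hypothesis test, so no decision rule can change. Total antipyretic use is reported beside the fever rate, so a reader sees how common it was. Treatment of symptoms stays allowed, so some masking remains under any wording. All of this stands, and it limits the weight of the point. It does not reconcile the texts, because discouraged use is still permitted use.

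One might also read the visit wording as meant for routine vaccines given at the same visit, which 6.1.3 and 6.5.2 allow. The wording names no such purpose, so it takes in the case that 6.5.1 bars. The scope of 6.5.1 does limit the fix, though: the replacement text should not ban more than 6.5.1 does.

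The sponsor could instead soften 6.5.1 to match the other four places. That would also remove the contradiction. The delay rule and the treatment-only permission in 6.5.2 and SAP 3.6.2 favour keeping the ban, but the choice is the sponsor's.

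**Conclusion.** The contradiction is certain and current, and it is worth fixing because following the procedures as written allows conduct that touches a primary safety outcome. It is confined in practice to prophylaxis after the dose. That it would lower observed fever, pain and irritability rests on the assumption that such medication works as intended. The size cannot be determined from the documents.

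Three stronger readings are tempting and are not supported:

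- A reader might infer that the whole safety profile is pushed toward looking milder. It is not one-directional, because antipyretic use is part of the same estimand and would rise.
- A reader might put assumed values into the formula and treat the resulting shift in fever as the impact. Every input would be an assumption, and the result would count all prophylaxis rather than the part that the wording causes.
- A reader might infer that infants given prophylaxis must drop out of the primary rSBA analysis. SAP Section 4 leaves criterion 5 to clinical review, so exclusion is not automatic. What is missing is guidance for that review.

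**What to change.** 1. In Protocol 1.3 footnote c, 8.11.1, 8.11.3 and SAP Table 4 footnote c, replace the permissive wording with a statement that matches 6.5.1. For example: *prophylaxis against reactions to the study vaccine is not allowed, whether before or after the injection; treating symptoms is allowed (Section 6.5.2)*. This also removes the limit to the vaccination day, which 6.5.1 does not have.
2. In SAP Section 4, add that e-diary antipyretic use alone does not trigger evaluable-set criterion 5, because the reason for use is not recorded.
3. Optionally, tabulate antipyretic use on days with no recorded fever or other symptom, for each dose, and label it a proxy. The daily variables already exist.

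The cost is a small protocol amendment, with IRB/EC review as required under 10.1.1, and a SAP edit. If the consent document carries the same sentence, it would need updating, and 10.1.3 then calls for reconsent. No participants, visits or data items are added.

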#### 6.5.2. Permitted During the Study

- Nonstudy vaccines used in the event of a disease outbreak or pandemic are allowed. However, while prioritizing standard clinical care, efforts should be made not to administer nonstudy vaccines within 14 days (for nonlive vaccines) or 28 days (for live vaccines) prior to study vaccine administration, as specified below.
- Nonstudy vaccines (other than meningococcal vaccine groups A, C, W, or Y) that are part of recommended immunization schedules are allowed any time during the study but should not be administered within 14 days (for nonlive vaccines) and 28 days (for live vaccines) of study vaccine administration. Tetanus-containing vaccines are allowed any time during the study (and can be given at the same time as study vaccine) but should not be administered within 30 days before study vaccine administration.
- Antipyretics and other pain medications to treat symptoms associated with the investigational product are permitted.
- A local anesthetic may be used at the site of the blood draw.
- Topical antibiotics are permitted.
- Topical and inhaled corticosteroids are permitted.

#### 6.5.3. Prohibited Prior Treatments

Receipt of any blood products, including immunoglobulin, prior to the first study vaccine administration is prohibited.

#### 6.6. Dose Modification

Not applicable.

# 6.7. Intervention After the End of the Study

No intervention will be provided to study participants at the end of the study.

# 7. DISCONTINUATION OF STUDY INTERVENTION AND PARTICIPANT DISCONTINUATION/WITHDRAWAL

# 7.1. Discontinuation of Study Intervention

In rare instances, it may be necessary for a participant to permanently discontinue study intervention (definitive discontinuation). Reasons for definitive discontinuation of study intervention include the following: AEs, parent(s)/legal guardian(s) request, and protocol violation.

Note that discontinuation of study intervention does not represent withdrawal from the study. If study intervention is definitively discontinued, the participant will remain in the study to be evaluated for collection of safety information. See the SoA for data to be collected at the time of discontinuation of study intervention and follow-up for any further evaluations that need to be completed.

In the event of discontinuation of study intervention, it must be documented on the appropriate CRF/in the medical records whether the participant is discontinuing further receipt of study intervention or also from study procedures, posttreatment study follow-up, and/or future collection of additional information.

# 7.2. Participant Discontinuation/Withdrawal From the Study

A participant may withdraw from the study at any time at his/her own request. Reasons for discontinuation from the study include the following:

- Withdrawn consent (refused further follow-up);
- Lost to follow-up;
- Medication error without associated AE;
- Death;
- Study terminated by sponsor;
- AEs;
- Protocol violation;
- No longer meets eligibility criteria.

If a participant does not return for a scheduled visit, every effort should be made to contact the participant's parent(s)/legal guardian(s). All attempts to contact the parent(s)/legal guardian(s) and information received during contact attempts must be documented in the participant's source document. In any circumstance, every effort should be made to document participant outcome, if possible.

The parent(s)/legal guardian(s) should be questioned regarding the reason for the participant's withdrawal. The investigator or his or her designee should capture the reason for withdrawal in the CRF for all participants.

If a participant withdraws from the study, the parent(s)/legal guardian(s) may request destruction of any remaining samples taken and not tested, and the investigator must document any such requests in the site study records and notify the sponsor accordingly.

The parent(s)/legal guardian(s) should be requested to have the participant return for a final visit, if applicable, and the investigator will perform the procedures indicated for the next visit. Any AEs or SAEs that are continuing at the time of withdrawal from the study should be followed until resolution or, in case of permanent impairment, until the condition stabilizes.

If the participant withdraws from the study and his/her parent(s)/legal guardian(s) also withdraws consent (see Section 7.2.1) for disclosure of future information, no further evaluations should be performed and no additional data should be collected. The sponsor may retain and continue to use any data collected before such withdrawal of consent.

When a participant withdraws from the study because of an SAE, the SAE must be recorded on the CRF and reported on the Vaccine SAE Reporting Form.

Lack of completion of all or any of the withdrawal/early termination procedures will not be viewed as protocol deviations so long as the participant's safety was preserved.

Participants who have received the investigational product will not be replaced regardless of the reason for withdrawal.

#### 7.2.1. Withdrawal of Consent

Participants whose parent(s)/legal guardian(s) requests the participant discontinues receipt of study intervention will remain in the study and must continue to be followed for protocol-specified follow-up procedures. The only exception to this is when a participant's parent(s)/legal guardian(s) specifically withdraws consent for any further contact with him or her or persons previously authorized by the participant's parent(s)/legal guardian(s) to provide this information. The participant's parent(s)/legal guardian(s) should notify the investigator in writing of the decision to withdraw consent from future follow-up, whenever possible. The withdrawal of consent should be explained in detail in the medical records by the investigator, as to whether the withdrawal is only from further receipt of study intervention or also from study procedures and/or posttreatment study follow-up, and entered on the appropriate CRF page. In the event that vital status (whether the participant is alive or dead) is being measured, publicly available information should be used to determine vital status only as appropriately directed in accordance with local law.

# 7.3. Lost to Follow-up

A participant will be considered lost to follow-up if he or she repeatedly fails to return for scheduled visits and the participant's parent(s)/legal guardian(s) is unable to be contacted by the study site.

The following actions must be taken if a participant's parent(s)/legal guardian(s) fails to return to the clinic for a required study visit or cannot be reached by telephone:

- The site must attempt to contact the participant's parent(s)/legal guardian(s) and reschedule the missed visit as soon as possible and counsel the participant's parent(s)/legal guardian(s) on the importance of maintaining the assigned visit schedule and ascertain whether or not the participant's parent(s)/legal guardian(s) wishes to and/or should continue in the study;
- Before a participant is deemed lost to follow-up, the investigator or designee must make every effort to regain contact with the participant's parent(s)/legal guardian(s) (where possible, 3 telephone calls and, if necessary, a certified letter to the participant's last known mailing address or local equivalent methods). These contact attempts should be documented in the participant's medical record;
- Should the participant's parent(s)/legal guardian(s) continue to be unreachable, he/she will be considered to have withdrawn from the study.

